6 STUDY INTERVENTION

6.1 STUDY INTERVENTION(S) ADMINISTRATION

6.1.1 STUDY INTERVENTION DESCRIPTION

We will be using the XCSITE100 stimulator designed by PulvinarNeuro in the [name] Lab for investigational purposes. The device is not implanted and has not been designed for or being used to support or sustain human life. This device does not have a potential for serious risk to the health, safety, or welfare of the participant. There has never been an instance of serious side-effect reported due to the use of transcranial brain stimulation. Previous studies in the [name] lab that used comparable devices (i.e., the commercial, CE-certified Neuroconn Plus stimulator) have always been classified as “non-significant risk” by the full UNC IRB. The Neuroconn Plus stimulator and the XCSITE100 stimulator are electrically equivalent and provide the same stimulation. While the Neuroconn device is commercially available, it cannot be preprogrammed for 10Hz-tACS, cannot be monitored remotely, and is not designed for tACS clinical trials. This makes the use of the Neuroconn device not appropriate for this study.

The XSCITE100 stimulator may apply tACS for up to 40 minutes (2400 seconds) with appropriate current ramp-up at the beginning of stimulation and ramp-down at the end of stimulation. tACS may be applied for currents between 100 μ A and 2 mA (peak-to-peak for tACS). For the purposes of this study, this device will be set to deliver either sham stimulation, alpha-tACS, or theta-tACS.

The XCSITE100 device runs on a single 9V rechargeable battery. The device itself is run through a device on a tablet. For more instructions, please see attached instruction manual.

The stimulator has two main components:

1. Android tablet with user interface application (i.e., App)
2. Stimulator with:
 1. Microprocessor
 2. Function generator chip
 3. Voltage controlled current source
 4. Safety circuitry

6.1.2 DOSING AND ADMINISTRATION

The research team will first measure each participant's head using the 10-20 system to determine the electrode locations. Participants will then be fitted with the 3 electrodes for stimulation: two 5x5cm

electrodes placed over F3 and F4, and one 5x7cm electrode placed on Cz. Electrodes will be carbon rubber, with Ten20 conductive paste applied. During stimulation, the participant will be in a relaxed and experimentally-controlled state by watching a nature movie (such as *Reefscapes*). One session of stimulation will be performed per patient per day, for 40 minutes. Before and after the stimulation on Day 1 and Day 5 of stimulation, an eyes open resting state EEG will be performed.

Participants will be randomly assigned to one of three arms; active sham stimulation, individualized alpha-tACS (usually 8-12Hz), or individualized theta-tACS (alpha frequency minus 4 Hz). Active sham stimulation will include 20 seconds of ramp-in to 40 seconds of 10 Hz tACS with a ramp out of 20 seconds for a total of 80 seconds of stimulation. The choice of an active sham is motivated to enhance success of patient blinding by mimicking skin sensations associated with tACS. Alpha- tACS and theta-tACS will have a 20 second ramp-in and ramp-out with 40 minutes of stimulation for a total of 2440 seconds of stimulation. Stimulation waveform is a sine-wave with a zero-to-peak amplitude of 1 mA. In each arm, participants will stay in a relaxed and yet controlled state by watching a nature movie such as "Reefscape" during stimulation.

Stimulation devices will be preprogrammed and codes will be randomized to one of the two experimental arms. Researchers will enter the participant-specific code into the Asus tablet that controls the XCSITE100 device and will monitor participants during the 40 minutes of the stimulation. The study coordinator and/or the research assistant will be thoroughly trained and have trainings documented on the transcranial stimulation device and will be present during all stimulation sessions. To monitor side effects of stimulation an adverse events questionnaire will be administered after each stimulation session.

Adverse Effects Questionnaire:

Transcranial Current Stimulation Questionnaire

Did you experience any of the following? Please circle the appropriate number for each (1-4). In the last column, indicate how related the symptom is to transcranial current stimulation

1 = no relation; 2 = remote; 3 = possible; 4 = probable; 5 = definite

	Absent	Mild	Moderate	Severe	Related to Stimulation?
Headache:	1	2	3	4	
Neck pain:	1	2	3	4	
Scalp pain:	1	2	3	4	
Tingling:	1	2	3	4	
Itching:	1	2	3	4	
Ringing/Buzzing Noise:	1	2	3	4	
Burning sensation:	1	2	3	4	
Local redness:	1	2	3	4	

Lupus Brain		Version 1.8
Protocol		4 March 2022

Sleepiness:	1	2	3	4
Trouble concentrating:	1	2	3	4
Improved mood:	1	2	3	4
Worsening of mood:	1	2	3	4
Dizziness:	1	2	3	4
Flickering lights:	1	2	3	4
Other (specify):	1	2	3	4

6.2 MEASURES TO MINIMIZE BIAS: RANDOMIZATION AND BLINDING

6.2.1 RANDOMIZATION

[name] will randomize 72 6-digit codes which will be used by the study coordinator and research assistants. These codes are directly linked to which treatment participants receive (sham/placebo, individualized alpha-tACS at 1 mA, or theta-tACS at 1 mA) and will be entered into the XCSITE tablet. The assignment of each participant cannot be determined by looking at the codes (e.g., codes are not sequential, code assignment is not based on “odd” or “even” numbers). [name] has no other responsibility in the study other than providing these randomized codes. In the case that [name] leaves the [name] Lab, another equivalent researcher who does not work with human participants will perform this task.

In case of attrition, previously used codes will be used for newly randomized participants. If a participant withdraws, is withdrawn, or is lost to follow up, the codes will be reassigned.

6.2.2 BLINDING

This study is designed to be double-blind. This means that the participant and the researchers do not know of each participant's assignment until the completion of all data collection. This is accomplished by the use of the randomization codes described above.

Furthermore, this study utilizes an active sham stimulation. This means that the sham/placebo condition includes some stimulation, mimicking the skin sensations associated with tACS. In our previously concluded trial (Alexander et al., 2019), participants in the sham and 10 Hz tACS groups responded similarly to the blinding questionnaire, indicating that our active sham stimulation successfully blinded the participants.

Additionally, during the initial data analysis phase, [name] will be blinded to whether data and results are from sham vs active treatment in compliance with the UNC School of Medicine Conflict of Interest Committee proposed financial conflict of interest management plan.

6.3 STUDY INTERVENTION COMPLIANCE

Full compliance with the intervention is defined as completing all 5 daily stimulation sessions for 40 minutes each day. As the intervention is applied and monitored by the study coordinator(s) and research assistants, compliance can be directly observed.

6.4 CONCOMITANT THERAPY

Eligible participants will be permitted to be receiving concomitant therapy. The only medications not permitted during this trial are anticonvulsants and benzodiazepines. While the use of antidepressants, anti-inflammatories, or other therapies may improve the symptoms of SLE during the course of this study, we anticipate that this bias will be reduced by two factors: (1) prior to entry to the study, all participants will be required to be on stable SLE and psychiatric related medications (i.e., no change in administration or dose) for at least 4 weeks, and (2) the design of this study includes a control stimulation (placebo/sham). Both of these design choices will reduce the potential outside influence of concomitant therapies.

To ensure that concomitant therapies are logged appropriately, participants will be requested to report any changes to the researchers. Furthermore, concomitant therapies will be logged at the Initial Session, Day 1 of stimulation (baseline), day 5 of stimulation, and at both follow-up visits. Participants will be requested to include the dosing for these therapies (i.e., how often per day, how much in each pill, how many pills) as well as when they were first prescribed the medication.

7 STUDY INTERVENTION DISCONTINUATION AND PARTICIPANT DISCONTINUATION/WITHDRAWAL

7.1 DISCONTINUATION OF STUDY INTERVENTION

Discontinuation from the week of stimulation does not mean discontinuation from the study, and remaining study procedures should be completed as indicated by the study protocol. If a clinically significant finding is identified (including, but not limited to changes from baseline) after enrollment, the investigator or qualified designee will determine if any change in participant management is needed. Any new clinically relevant finding will be reported as an adverse event (AE).

The study intervention (i.e., the 5 consecutive days of stimulation) will be discontinued for the following reasons:

- A participant develops increased suicidal risk, as determined by an acute assessment by [name].
- A participant has a YMRS score greater than to 12.
- The participant misses two consecutive days of stimulation.
- The participant misses a single day of stimulation and is unable to make it up at the end of the stimulation week.
- Any clinical adverse event (AE), laboratory abnormality, intercurrent illness or other medical condition, or situation occurs such that continued participation in the study would not be in the best interest of the participant.
- The participant meets any exclusion criteria (either newly developed or not previously recognized).
- A participant wishes to withdraw from further participation for any reason.

If the participant withdraws from the intervention, he/she will be followed through the 4 week follow-up with the designated clinical assessments to ensure participant safety:

- HDRS
- YMRS
- Suicide Questionnaire

Additional measures may be continued if deemed appropriate (e.g., EEG, cognitive tasks, Comparative Pain Scale, Pain Catastrophizing Scale).

7.2 PARTICIPANT DISCONTINUATION/WITHDRAWAL FROM THE STUDY

A study participant will be discontinued from further participation if:

- Any clinical adverse event (AE), serious adverse event (SAE), laboratory abnormality, intercurrent illness or other medical condition, or situation occurs such that continued participation in the study would not be in the best interest of the participant.
- The participant meets any exclusion criteria (either newly developed or not previously recognized).
- A participant wishes to withdraw from further participation for any reason.

The reason for participant discontinuation or withdrawal from the study will be recorded with the participant files. Participants who sign the informed consent form and are not randomized will be replaced. Participants who sign the informed consent form, and are randomized and receive the full study intervention (5 consecutive days of 40 minutes of stimulation), and subsequently withdraw or are withdrawn or discontinue from the study will not be replaced. However, participants who sign the informed consent form, and are randomized and receive only part of the study intervention, and subsequently withdraw or are withdrawn or discontinue from the study will be replaced.

7.3 LOST TO FOLLOW-UP

All efforts will be made to ensure participants are not lost to follow-up, including developing rapport and ensuring enrolled participants are reminded of their session dates. To ensure that participants attend both follow-up sessions, study coordinators and research assistants will be flexible in timing, including offering sessions later in the day as well as some weekends.

Every effort will be made to contact participants who are lost to follow-up, including contacting via email and phone. However, if a participant is lost to follow-up, the missed sessions will be labeled as missing data and our pre-determined analysis plan takes into consideration missing data.

7.4 SUSPENSION OR TERMINATION OF STUDY

This study may be temporarily suspended or prematurely terminated if there is sufficient reasonable cause.

Circumstances that may warrant termination or suspension include, but are not limited to:

- Determination of unexpected, significant, or unacceptable risk to participants
- Insufficient compliance to protocol requirements
- Data that are not sufficiently complete and/or evaluable
- 2 SAEs for up to 10 participants or 20% SAE if more than 10 (see SAE stopping rules below)
- 6 TEAEs for up to 10 participants or 40% TEAE if more than 10 (see TEAE stopping rules below)

If the study is prematurely terminated or suspended, the Principal Investigator (PI) will promptly inform research staff, study participants, the DSMB and the IRB and will provide the reason(s) for the termination or suspension. Study participants will be contacted, as applicable, and be informed of changes to study visit schedule.

Study may resume once concerns about safety, protocol compliance, and data quality are addressed.

7.4.1 SERIOUS ADVERSE EVENT (SAE) STOPPING RULES

In the event of 2 SAEs (if enrollment is less than 10 subjects), possibly or definitely associated with the study intervention, the study will be suspended and the DSMB will be notified. If enrollment is more than 10 subjects, in the event of the equivalent SAEs to 20% of study enrollment, possibly or definitely associated with the study intervention, the study will be suspended and the DSMB will be notified.

7.4.2 TREATMENT EMERGENT ADVERSE EVENT (TEAE) STOPPING RULES

The use of tACS is known to have transient, mild to moderate AEs, including phosphene perception, dizziness, skin sensation, mild headache, vertigo, pressure perception, and back pain and neck stiffness.

For the purposes of this study, a treatment-emergent adverse event (TEAE) is defined as a new event that occurs during or after first dose of study treatment that persists for 14 days or more (ie: event occurs during stimulation week and continues to persist at 2 week follow up) and is determined to be related to the study intervention.

The study will be suspended and the DSMB will be notified for TEAEs possibly or definitely related to intervention:

- in the event of 6 TEAEs (for enrollment up to 10 subjects);
- in the event of the equivalent TEAEs to 40% of study enrollment, if enrollment is more than 10 subjects

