1.2.1 ARM ALLOCATION

Up to 72 participants will be equally randomized in to one of three arms (1:1:1):

**Randomization is double-blind

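### The two halves of the TEAE suspension rule do not join: 6 events is 60% at 10 enrolled, but from 11 enrolled the trigger is 40%, so the required count falls

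*Combined protocol and SAP*

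**What the plan says.** Section 7.4.2 defines a TEAE for this study as a new, intervention-related event that starts during or after first treatment and lasts at least 14 days. It then makes suspension automatic: "The study will be suspended and the DSMB will be notified for TEAEs possibly or definitely related to intervention". The trigger has two parts: "in the event of 6 TEAEs (for enrollment up to 10 subjects", and "in the event of the equivalent TEAEs to 40% of study enrollment, if enrollment is more than 10 subjects". Section 7.4 repeats both figures in its list of circumstances that may warrant suspension or termination: "6 TEAEs for up to 10 participants or 40% TEAE if more than 10".

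The same list gives a serious adverse event (SAE) rule of the same shape: "2 SAEs for up to 10 participants or 20% SAE if more than 10". Sections 7.4.1 and 9.4.6 restate the SAE rule, but there the first part applies below 10 enrolled and the second above 10.

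The document gives no reason for the change of rate in the TEAE rule, no rounding rule for the percentage, and no statement on whether several events in one participant count once or more than once.

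**The concern.** A fixed count for small numbers followed by a percentage for larger numbers is a common form of stopping rule. It works without surprises when the two parts agree where they meet. Here they do not. The required count falls as enrolment passes 10, so the rule can stay silent at a higher event rate and fire at a lower one. It can also fire because a participant enrolled rather than because an event occurred.

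This matters because Section 7.4.2 is worded as an instruction: when the count is reached, the study is suspended and the DSMB is told. Scheduled DSMB review is every 6 months (Sections 9.4.6 and 10.1.6), so between reviews this count is one of the few numerical safety triggers that staff must apply. They should be able to apply it without deciding for themselves what was meant.

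**Working it through.** **Inputs.** TEAE rule: 6 events up to 10 enrolled and 40% of enrolment above 10 (Sections 7.4 and 7.4.2). SAE rule: 2 events and 20% (Section 7.4). Maximum enrolment: 72 (Section 1.2.1, "Up to 72 participants will be equally randomized in to one of three arms").

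**Step 1. Does the fixed count follow from the percentage?**
- TEAE: 0.40 × 10 = 4, whereas the stated count is 6, and 6/10 = 60%. The 6 is not reproduced from the 40%.
- SAE: 0.20 × 10 = 2, and the stated count is 2. The figures agree at 10.

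**Step 2. Required TEAE count by enrolment n.** Up to 10 it is 6. Above 10 it is 0.40 × n, made a whole number. The plan does not say how, so all three conventions are shown.

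| n | 0.40 × n | rounded up (at least 40%) | nearest | rounded down |
|---|---|---|---|---|
| 10 | fixed | 6 | 6 | 6 |
| 11 | 4.4 | 5 | 4 | 4 |
| 12 | 4.8 | 5 | 5 | 4 |
| 13 | 5.2 | 6 | 5 | 5 |
| 14 | 5.6 | 6 | 6 | 5 |
| 15 | 6.0 | 6 | 6 | 6 |
| 16 | 6.4 | 7 | 6 | 6 |

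The count falls between 10 and 11 under every convention: by one event when rounding up, by two otherwise. It stays below 6 at n = 11 to 12 (up), 11 to 13 (nearest) or 11 to 14 (down).

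**Step 3. The same five events on either side of the boundary.**
- n = 10: 5/10 = 50%, and 5 < 6, so the rule does not fire.
- n = 11: 5/11 = 45.5%, and 5 meets the count under every convention, so the rule fires.
- n = 12: 5/12 = 41.7%, and the rule fires.

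The percentages are events per enrolled participant, because the rule as written counts events.

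**Step 4. The SAE rule at the same point.** 0.20 × 11 = 2.2, which is 3 rounded up and 2 otherwise. From 2 at n = 10 the count rises or stays level; it does not fall. At exactly 10 enrolled, however, Sections 7.4.1 and 9.4.6 state no rule, because one part is for fewer than 10 and the other for more than 10.

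**Step 5. Illustration of size.** The documents give no TEAE rate. Assume independent participants, at most one TEAE each, and a per-participant probability p. The binomial chance of meeting the threshold is then:

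| p (assumed) | n = 10, at least 6 | n = 11, at least 5 (rounded up) | n = 11, at least 4 |
|---|---|---|---|
| 0.1 | 0.0001 | 0.0028 | 0.0185 |
| 0.2 | 0.0064 | 0.0504 | 0.1611 |
| 0.3 | 0.0473 | 0.2103 | 0.4304 |
| 0.4 | 0.1662 | 0.4672 | 0.7037 |

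One additional participant multiplies the chance of meeting the threshold several times over, with no change in the underlying risk.

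**The case against.** Much can fairly be said for the plan.

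- **The 6 need not be a miscalculation.** A reader might infer that 6 is a slip for a figure derived from 40%. The document never says that the 6 was derived that way. The amendment history records that the suspension rules were updated and specified at version 1.7, apparently at the DSMB's request, so a deliberate choice cannot be excluded. This stands: what can be shown is an unexplained mismatch, not an error of arithmetic.
- **A fixed count is always a larger share of a smaller number.** A reader might infer that the rule is wrong because it is lenient early. The SAE rule has the same property: 2 of 5 is 40%, against 20% later. The share below 10 is therefore not the defect; only the failure to join is.
- **The study is not obliged to continue at 5 events among 10.** Section 7.4 says that its grounds for suspension are not exhaustive and separately lists unacceptable risk. Section 10.1.6 has the principal investigator or co-investigator review adverse events in real time. Only this automatic trigger stays silent.
- **The range is narrow and the effect cautious.** When rounding up, the dip covers two enrolment values and one event, in a trial of up to 72. Firing suspends the study and informs the DSMB, and Section 7.4 allows it to resume. Events must last at least 14 days, so counts lag enrolment.
- **The SAE rule is not a clean model.** Its figures agree at 10, but its detailed wording leaves exactly 10 uncovered.

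These points limit the size of the problem. None of them explains or removes the fall in the count at 11 enrolled.

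**Conclusion.** The point holds as an internal inconsistency. Sections 7.4 and 7.4.2 agree with each other, but the two halves of the rule do not: 60% at 10 enrolled, 40% above. The fall in the required count from 10 to 11 does not depend on rounding. The count of 5 at 11 and 12 enrolled does, since it assumes that 40% means at least 40%; the other conventions give 4 at 11. Five TEAEs among 10 leave the automatic rule silent and the same five among 11 trigger it, whichever convention is used.

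The practical reach is small: two to four enrolment values, depending on rounding, with discretionary safeguards in place throughout. The documents do not give current enrolment; if it is well past 10, the early clause has little remaining effect. The conclusion does not extend to saying that the early figure is too high, that the later one is too low, or that participants would go unprotected. The documents support only that the two figures must be reconciled.

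**What to change.** The study team and the DSMB should reconcile the fixed count and the percentage, and carry the agreed wording into both Section 7.4 and Section 7.4.2. If the change of rate at 10 is intended, the protocol should say so and give the reason. The same amendment should state how the percentage is turned into a whole count, and whether the rule counts events or participants with at least one event. While the text is open, the SAE wording in Sections 7.4.1 and 9.4.6 should be brought into line with Section 7.4, so that exactly 10 enrolled is covered. Which TEAE figure is right is for the study team and the DSMB to decide.

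The cost is a short wording amendment with the usual IRB approval, and DSMB confirmation of the intended rule. No data collection or analysis changes.

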Risk of Injury and Discomfort: The side effects of tACS are mild and transient; in fact, low intensity transcranial current stimulation, such as tACS, has been used for several years without any report of serious side effects ([name] & McCormick, 2010). Furthermore, this stimulation mode has nothing to do with electroconvulsive therapy that applies many orders of magnitude higher stimulation current. Rather, transcranial current stimulation is so weak that it does not cause super-threshold activation of neurons (Khan, Khan, Shankles, & Polissar, 2002). However, tACS does have some mild side effects, such as transient mild tingling, burning, or itching under the electrode sites. In the first part of this study, participants from all three groups reported either absent or mild side effects and there was no difference between the groups with the exception of "flickering lights" (or phosphene, $p = 0.014$) (Alexander et al., 2019). In order to monitor these, we will be administering an adverse effects stimulation questionnaire after each stimulation session to determine whether these effects were experienced and at what intensity. Research personnel present during these sessions will also check in with the participant periodically during the stimulation to see whether they are comfortable. If participant is experiencing severe discomfort (as determined by the adverse effects questionnaire or by self-report), the stimulation will be immediately stopped.

Risks associated with emotional distress in case of incidental findings on structural MRI or a false positive pregnancy test.

Risks associated with venous blood draw include minimal discomfort and/or bruising. Infection, excess bleeding, clotting, and fainting are also possible, although unlikely.

Patients experiencing depression have a higher risk of suicide. We have no evidence that our treatment paradigms will in any way increase this likelihood. In a similar study in patients with major depressive disorder (MDD), 4 participants in the sham/placebo stimulation group experienced an increase in suicidal thoughts and only one of those 4 participants reported suicidal intent. No participants who

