8.2 SAFETY AND OTHER ASSESSMENTS

8.2.1 SAFETY

1. A suicide questionnaire previously used in IRBs #14-0600 and #14-1622 will be used at each session of this study. This questionnaire tracks suicidal ideation and behavior. Participants will be asked to answer whether they have had any thoughts of hurting themselves within the past 24 hours (suicidal ideation, SI) and whether they have hurt themselves within the past 24 hours (suicidal behavior, SB). If a participant admits to experiencing either SI or SB their participation will be stopped immediately and their primary mental health care provider or family physician will be contacted. In the case that they do not see anyone for their depressive symptoms, [name] will assist the participant in seeking medical care
2. The structural MRI to be used for source localization during EEG analysis will be conducted prior to randomization. The results of the T1 weighted sMRI will be reviewed by [name] for incidental findings of malignancy. If any are found, the study team will disqualify patient from study participation and will facilitate contact with providers for medical care per [name] recommendations. Patients will complete the provided MRI screening form provided by the Biological Research Imaging Center (BRIC) prior to the sMRI screening visit.
3. A stimulation adverse effects questionnaire will be administered at the end of each stimulation session. This questionnaire will be used as a safety measure and to collect data on participant experience. This questionnaire has been used in all our previous tACS studies.

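### The 40% TEAE suspension rule pools all three arms, so lasting non-serious harm in one arm can stay below it; give the DSMB masked-arm counts routinely and define the counting unit

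*Combined protocol and SAP*

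**What the plan says.** Section 7.4.2 defines a TEAE as a new, treatment-related event that begins during or after the first stimulation and lasts at least 14 days. The study is suspended and the DSMB notified at 6 such events when up to 10 are enrolled, or "in the event of the equivalent TEAEs to 40% of study enrollment, if enrollment is more than 10 subjects". Section 7.4 gives the same rule in shorthand: "6 TEAEs for up to 10 participants or 40% TEAE if more than 10". Neither section sets a limit by arm or says whether one participant can contribute more than once. Section 1.2.1 allocates up to 72 participants 1:1:1, and the synopsis expects at least 45 with evaluable data.

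Under section 9.4.6 the DSMB receives blinded descriptive safety data every six months. A table of participant numbers by masked arm goes directly to the DSMB, but only where there is reason to look at unblinded information. Section 6.2.1 says that the person who generates the codes "has no other responsibility in the study other than providing these randomized codes".

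**The concern.** Section 2.3.1 itself raises the possibility of harm in one arm: theta stimulation could in theory worsen depression. Part of its answer is DSMB review of blinded data. A trigger with all three arms in the denominator dilutes a signal from one arm by a factor of three, and a report not split by arm is poorly placed to show the DSMB that it has a reason to ask for the split. At stake is how soon lasting, non-serious harm confined to one arm would be recognised. The unstated counting unit adds to this, because the same sentence behaves very differently when it counts events and when it counts people.

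**Working it through.** The 40% is a chosen threshold with no stated derivation, so there is no figure in the plan to reproduce. Inputs: trigger 40% of enrolment (7.4.2), ratio 1:1:1 (1.2.1), n = 45 and n = 72 (synopsis). I take enrolment to mean randomised participants. The documents give no expected TEAE rate, so the rates below are assumptions.

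**1. Trigger against one full arm.** Trigger = 0.40n rounded up; one arm = n/3.
- n=45: 0.40 × 45 = 18; 45/3 = 15; short by 3.
- n=72: 0.40 × 72 = 28.8, so 29; 72/3 = 24; short by 5.

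One event in every member of one arm is 1/3 = 33% of enrolment.

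**2. What closes the shortfall when the whole arm is affected.**
- Other arms: 3/30 = 10% affected at n=45; 5/48 = 10.4% at n=72.
- Several events each: 18/15 = 1.20 per harmed-arm participant; 29/24 = 1.21.
- Uneven enrolment: codes of withdrawn participants are reused (6.2.1) and partial completers are replaced (7.2), so replacements enter the same arm. Suppose 15 completers per arm and 25% dropout in the harmed arm only. That arm then enrols 15/0.75 = 20 of 20 + 15 + 15 = 50, which is 40%. If all 20 are affected, the trigger is met exactly.

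**3. Probability that the pooled rule is met: single look, equal arms, each participant counted once.** Exact binomial, one arm at rate p1 and the other two at p2.

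| p1 | p2 | n=45 | n=72 |
|---|---|---|---|
| 100% | 0% | 0 | 0 |
| 100% | 5% | 19% | 9% |
| 100% | 10% | 59% | 53% |
| 100% | 20% | 96% | 98% |
| 80% | 5% | 1.9% | 0.3% |
| 80% | 10% | 13% | 6% |
| 80% | 20% | 57% | 53% |
| 50% | 20% | 9% | 3% |

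**4. The same rule checked after each participant from the 11th.** Simulation: 72 codes, 24 per arm, in random order; the first 45 or all 72 used; 0 to 4 participants with 14-day status pending. Repeated looks and chance imbalance raise the probabilities.
- Counted once per participant, 100% in one arm and 0% elsewhere: 0.23–0.57.
- 80% in one arm: 0.15–0.41 with 5% elsewhere, about 0.30–0.58 with 10%, and 0.67–0.88 with 20%.
- 50% in one arm: 0.02–0.09 with 5% elsewhere, and 0.19–0.42 with 20%.
- Counted as events (Poisson, mean 0.05 elsewhere): 0.07–0.17 at a mean of 0.5 events per harmed-arm participant, 0.59–0.77 at 1.0, and 0.93–0.99 at 1.5.

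The simulation does not model code reuse after withdrawal, so it may understate how often the rule fires when harm causes dropout.

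**5. SAE rule for comparison (7.4.1, 20%).** 0.20 × 45 = 9, or 9/15 = 60% of one arm; 0.20 × 72 = 14.4, so 15, or 15/24 = 62.5%. One arm alone can reach this limit.

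**The case against.** A reader might infer that the TEAE rule can never respond to harm in one arm. The documents do not support that. Section 7.4.2 literally counts events with no cap per participant, and the questionnaire covers 14 effects (9.4.4), so several lasting events per person could count. Code reuse after withdrawal can lift a harmed arm above one third. With 10–20% affected elsewhere, the pooled rule becomes much more responsive to severe one-arm harm. All of this stands, and it is why 33% is a stated case and not a ceiling.

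A reader might also infer that such harm would go unseen. That too goes beyond the text:
- Section 8.3.2 makes any grade 3 or higher event an SAE, so only milder lasting effects depend on the TEAE rule.
- Section 8.3.5 sends unexpected suspected serious reactions to the DSMB within 24 or 48 hours.
- Section 10.1.6 has the investigators reviewing AEs in real time.
- Section 8.2.1 has a fixed stop for individuals: "If a participant admits to experiencing either SI or SB their participation will be stopped immediately".
- Section 7.4 lists its suspension grounds as non-exhaustive.
- The DSMB could treat 15 lasting related events among 45 participants as reason enough to request the masked table.
- The amendment history for version 1.7 lists an update to the suspension rules and mentions a DSMB request in the rationale column.

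High TEAE rates are stress cases in any event. Of the earlier depression trial, section 2.3.1 says that "participants from all three groups reported either absent or mild side effects".

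What survives is narrower. None of these measures gives the DSMB routine counts by arm, and the study team doing the real-time review is blinded.

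**Conclusion.** The point holds in limited form. With equal arms and one event per participant, universal lasting harm in one arm and none elsewhere falls 3 events short at n=45 and 5 short at n=72. At a 50% rate in one arm and 5% elsewhere, counted once per participant, even continuous checking meets the rule in at most about one trial in ten. These sizes rest on assumed TEAE rates and on the counting unit; counted as events, the rule usually fires at a mean of one event per harmed-arm participant.

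Two further inferences are tempting and not supported. One is that the SAE rule needs the same repair. It needs about 60% of one arm, but serious reactions have their own expedited route, so 7.4.1 can stay as it is. The other is that a numeric within-arm trigger is required. The documents give no expected TEAE rate from which to set one, so it remains a choice for the DSMB.

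**What to change.** - **9.4.6:** make the existing masked-arm table a standing part of each six-monthly DSMB report, showing TEAE and SAE counts and the number of participants affected by masked arm. The code holder sends it directly to the DSMB, so the study team stays blind.
- **6.2.1:** add this duty, since the present text gives the code holder no other role.
- **7.4.2:** state whether the 40% counts events or participants with at least one TEAE.
- **7.4.1:** no change.

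Optional, if the DSMB wants a number: review when at least 40% of a masked arm, and at least 4 participants, are affected (6 of 15; 10 of 24). In simulation at four six-monthly reviews, this detects a 50% rate in one arm with probability 0.84–0.91. It also pauses the trial by chance in about 0.1–0.2%, 1–2%, 6–10% or 19–26% of trials when every arm's rate is 5%, 10%, 15% or 20%. The last figure is a good reason to leave the value to the DSMB.

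The cost is three wording edits, one extra table per report, a small duty for the code holder, and some DSMB queries prompted by chance variation in small arms.
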